6.4 Other Efficacy Analyses

The following additional efficacy endpoints will be summarized and analyzed for the ITT population:

- The percentage of subjects with HCV RNA < LLOQ at each post-baseline visit in the Treatment Period (using data as observed);
- The percentage of subjects with SVR₄;
- Adherence to treatment;
- The percentage of subjects in the ITT population with virologic failure by baseline FibroTest score (≤ 0.75 or > 0.75);
- The percentage of subjects in the ITT population with on-treatment virologic failure by HCV genotype;

- The percentage of subjects in the ITT population with post-treatment relapse by HCV genotype.

In the above analyses, the percentage of subjects with a two-sided 95% Wilson score interval will be summarized. Imputations for missing data will be performed as described in Section 4.7 for SVR, where a missing response will be imputed as a failure after performing the described imputation. All other endpoints will be presented using data as observed.

A summary of the subjects who completed treatment and relapsed will be prepared displaying the number of subjects relapsing overall and by SVR visit window (within the SVR₄ window or within the SVR₁₂ window), including the subject number and the SVR visit window corresponding to the first occurrence of relapse. A similar listing will be prepared for subjects who prematurely discontinued treatment and relapsed after having HCV RNA < LLOQ at their Final Treatment Visit.

Descriptive statistics (mean, standard deviation, median, minimum, and maximum; number and percentage) will be presented for exposure during the treatment period. Compliance (adherence) will be calculated for each subject and summarized with the mean, median, standard deviation, minimum, and maximum for each treatment arm and overall. A listing of compliance for each subject will be provided. The percentage of compliant subjects will be summarized based on data as observed. An additional summary of the percentage of compliant subjects will be provided where subjects who are missing study drug accountability records will be imputed as non-compliant.

6.4.1 Resistance Analysis

The following resistance information will be analyzed for all available baseline samples from subjects in the study: 1) the prevalence of polymorphisms at signature amino acid positions or a key subset of amino acid positions at baseline identified by next-generation sequencing (NGS) will be compared to the appropriate subtype specific prototypic reference sequence; and, (2) a comparison of SVR₁₂ rates in subjects with or without

baseline variants will be conducted. For subjects not achieving SVR₁₂, treatment-emergent substitutions at post-baseline time points will be identified by NGS relative to the respective baseline sequence and to a subtype-specific reference sequence.

HCV Genotype/Subtype:

Phylogenetic analysis will be conducted on all available HCV sequences from baseline samples in order to accurately determine HCV subtype.

6.4.2 Patient Reported Outcomes

The EuroQoL-5 Dimensions-5 Level (EQ-5D-5L) is a health state utility instrument that evaluates preference for health status (utility). The 5 items in the EQ-5D-5L comprise 5 dimensions (mobility, self-care, usual activities, pain/discomfort, and anxiety/depression) each of which are rated on 5 levels of severity (no problems, slight problems, moderate problems, severe problems, unable to do/extreme problems). Responses to the 5 items encode a discrete health state which is mapped to a preference (utility) specific for different societies.^{4,5} Subjects also rate their perception of their overall health on a separate visual analogue scale (VAS).

Summary statistics (n, mean) at each visit and for change from baseline (n, mean, SD, minimum, and maximum) to each visit will be provided for EQ-5D-5L health index score and VAS score.

6.5 Efficacy Subgroup Analyses

The number and percentage of subjects with SVR₁₂ in the ITT and mITT populations will be presented for the following key subgroups:

- Baseline APRI (≤ 0.7 or > 0.7) and (≤ 0.5 or > 0.5);
- HCV genotype (1, 2, 3, 4, 5, or 6) and available subtype;
- Age (< 65 or ≥ 65 years) and (< 75 or ≥ 75 years);
- Baseline FibroTest score (≤ 0.75 or > 0.75);
- Adherence to treatment (yes/no).

The two-sided 95% Wilson score confidence interval will be produced if there are at least 10 subjects in the subgroup.

7.0 Safety Analyses

7.1 General Considerations

Safety analyses will be performed using the safety population.

7.2 Analysis of Adverse Events

Adverse events will be coded using the Medical Dictionary for Regulatory Activities (MedDRA). The actual version of the MedDRA coding dictionary will be noted in the clinical study report.

Treatment-emergent adverse events are defined as any adverse event (AE) with an onset date that is after the first dose of study drug and no more than 30 days after the last dose of study drug. Events where the onset date is the same as the study drug start date are assumed to be treatment-emergent. If an incomplete onset date was collected for an adverse event, the event will be assumed to be treatment-emergent, unless there is other evidence that confirms that the event was not treatment-emergent (e.g., the event end date was prior to the study drug start date).

The number and percentage of subjects with treatment-emergent adverse events will be tabulated by primary MedDRA System Organ Class (SOC) and preferred term (PT). The system organ classes will be presented in alphabetical order, and the preferred terms will be presented in alphabetical order within each system organ class.

Adverse Event Overview

An overview of AEs will be presented consisting of the number and percentage of subjects experiencing at least one event for each of the following AE categories:

- Any treatment-emergent adverse event;

- Treatment-emergent adverse events with a "reasonable possibility" of being related to DAAs (glecaprevir/pibrentasvir);
- Treatment-emergent adverse events of grade 3 or higher;
- Serious treatment-emergent adverse events;
- Serious treatment-emergent adverse events with a "reasonable possibility" of being related to DAAs (glecaprevir/pibrentasvir);
- Treatment-emergent adverse events leading to discontinuation of study drug;
- DAA-related treatment-emergent adverse events leading to discontinuation of study drug;
- Treatment-emergent adverse events of Grade 3 or higher with a "reasonable possibility" of being related to DAA (glecaprevir/pibrentasvir);
- Serious treatment-emergent adverse events leading to discontinuation of study drug;
- Treatment-emergent adverse events leading to interruption of study drug;
- Treatment-emergent adverse events leading to death;
- Deaths.

Adverse Events by SOC and PT

Subjects reporting more than one AE for a given PT will be counted only once for that term (most severe/highest grade incident for the severity tables and most related incident for the relationship tables). Subjects reporting more than one AE within an SOC will be counted only once for that SOC. Subjects reporting more than one AE will be counted only once in the overall total.

The following summaries of AEs by SOC and PT will be generated:

- Treatment-emergent adverse events;
- Treatment-emergent adverse events with a "reasonable possibility" of being related to DAAs (glecaprevir/pibrentasvir);
- Serious treatment-emergent adverse events;

- Serious treatment-emergent adverse events with a "reasonable possibility" of being related to DAAs (glecaprevir/pibrentasvir);
- Grade 3 or higher treatment-emergent adverse events;
- Treatment-emergent adverse events of Grade 3 or higher with a "reasonable possibility" of being related to DAA (glecaprevir/pibrentasvir);
- Treatment-emergent adverse events leading to discontinuation of study drug;
- DAA-related treatment-emergent adverse events leading to discontinuation of study drug;
- Serious treatment-emergent adverse events leading to discontinuation of study drug;
- Treatment-emergent adverse events leading to interruption of study drug;
- Treatment-emergent adverse events leading to death.

A listing of treatment-emergent adverse events grouped by body system and preferred term with subject numbers will be provided.

Adverse Events by PT

The number and percentage of subjects experiencing treatment-emergent adverse events will be tabulated according to PT and sorted by overall frequency. Similar summaries will be provided for Grade 3 or higher treatment emergent adverse events, DAA related treatment-emergent adverse events, DAA-related Grade 3 or higher treatment-emergent adverse events, and DAA-related treatment-emergent serious adverse events.

Adverse Events by Maximum Severity Grade Level

Treatment-emergent adverse events and DAA-related treatment-emergent adverse event will be summarized by maximum severity grade. Each adverse event will be assigned a grade level (grade 1, 2, 3, 4, or 5) by the investigator. If a subject has an AE with unknown severity, then the subject will be counted in the severity grade level category of "unknown," even if the subject has another occurrence of the same event with a severity present. The only exception is if the subject has another occurrence of the same AE with

the highest grade level (grade 5). In this case, the subject will be counted under the "Grade 5" category.

Adverse Event by Maximum Relationship

Treatment-emergent adverse events also will be summarized by maximum relationship of each preferred term to study drug (DAA), as assessed by the investigator. If a subject has an adverse event with unknown relationship, then the subject will be counted in the relationship category of "unknown," even if the subject has another occurrence of the same event with a relationship present. The only exception is if the subject has another occurrence of the same adverse event with a relationship assessment of "Reasonable Possibility." In this case, the subject will be counted under the "Reasonable Possibility" category.

Other Adverse Events

The number and percentage of subjects experiencing at least one treatment-emergent adverse event in the search defined by Product MedDRA Query (PMQ) "Hepatic Decompensation and Hepatic Failure" will be presented overall and by SOC and PT. In addition, a listing of treatment-emergent adverse events for subjects meeting the search criterion will be provided.

Listing of Adverse Events

The following listings of adverse events will be prepared:

- All serious adverse events (from the time the subject signed the study-specific informed consent through the end of the study),
- Treatment-emergent serious adverse events,
- Treatment-emergent adverse events leading to death,
- Treatment-emergent adverse events leading to discontinuation of study drug,
- Treatment-emergent adverse events leading to study drug interruption.

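### In the maximum-severity tables, a known Grade 3 or 4 adverse event is shown as unknown when another occurrence of the same event has no grade

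*SAP*

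**What the plan says.** All of the relevant text is in SAP 7.2, Analysis of Adverse Events.

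- **General counting rule** (under Adverse Events by SOC and PT). A subject with several events under one preferred term is counted once for that term, using the "most severe/highest grade incident for the severity tables and most related incident for the relationship tables".
- **Scope of the severity tables** (under Adverse Events by Maximum Severity Grade Level). "Treatment-emergent adverse events and DAA-related treatment-emergent adverse event will be summarized by maximum severity grade".
- **Expected completeness.** "Each adverse event will be assigned a grade level (grade 1, 2, 3, 4, or 5) by the investigator".
- **Rule for a missing grade.** A subject with an ungraded occurrence goes to the unknown category "even if the subject has another occurrence of the same event with a severity present". The exception begins "The only exception is if the subject has another occurrence of the same AE with" and ends "the highest grade level (grade 5). In this case, the subject will be counted under the 'Grade 5' category".
- **Separate severe-event summaries.** Grade 3 or higher treatment-emergent events, overall and drug-related, are also reported in the adverse event overview (as subjects with one or more such events), by SOC and preferred term, and by preferred term. The missing-grade rule appears only under the maximum-severity heading. Nothing extends it to these summaries.

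**The concern.** A blank field on one record removes an established severe grade from its row. For a subject with a Grade 3 occurrence and an ungraded one, it is certain that the maximum is at least Grade 3, yet the table reports that nothing is known.

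The general counting rule and the missing-grade rule both govern the severity tables and give different answers for such a subject. The SAP does not say that one is an exception to the other.

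The same subject can also be Grade 3 or higher in the overview and unknown in the maximum-severity table, so two tables in one report need not agree. Safety is part of the primary objective (Protocol 3.1, SAP 4.1) and few severe events are expected, so a mismatch of even one subject would be noticed and would need explaining.

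The rule also differs in spirit from other missing-data conventions in the SAP. An adverse event with an incomplete onset date is presumed treatment-emergent (SAP 7.2), and a subject with no HCV RNA value after imputation counts as a failure (SAP 4.7).

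**Working it through.** The plan states no figure on this point, so there is none to reproduce. The check has two parts: what the rules do, and how large the effect could be.

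**1. The rules side by side.** The missing-grade rule was applied as Grade 5 if present, otherwise unknown if any occurrence is ungraded, otherwise the maximum. The general rule was read as the highest known grade.

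| Occurrences of one event in one subject | Missing-grade rule | Highest known grade | In the Grade 3 or higher summaries? |
|---|---|---|---|
| Grade 3 and ungraded | unknown | Grade 3 | yes |
| Grade 4 and ungraded | unknown | Grade 4 | yes |
| Grade 5 and ungraded | Grade 5 | Grade 5 | yes |
| Grade 1 and ungraded | unknown | Grade 1 | no |
| Grade 3 and Grade 1 | Grade 3 | Grade 3 | yes |
| ungraded only | unknown | unknown | no |

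The first two rows are the problem: the two SAP sentences disagree, and the maximum-severity table disagrees with the Grade 3 or higher summaries. The fourth row (Grade 2 with ungraded behaves the same way) also shows the two sentences disagreeing, but no known severe grade is lost there.

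**2. Scale.** Inputs from the documents:
- planned enrolment of 230 (SAP 4.4);
- Grade 3 or higher adverse events in 3.8% of subjects in the earlier programme (Protocol 2.2).

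Input assumed, because the documents give none: the share *u* of Grade 3 or higher subjects who also have an ungraded occurrence of the same event, taken as 1% to 20%. It is further assumed that a moved subject has no other fully graded Grade 3 or higher event that would keep the subject in those rows.

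- Expected Grade 3 or higher subjects: 230 × 0.038 = 8.74.
- Expected number moved to unknown: 8.74 × *u*.
- Grade 3 or higher rate left in the maximum-severity table: 3.8% × (1 − *u*).
- Chance that at least one subject is moved: 1 − (1 − 0.038 × *u*)^230.

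| *u* (assumed) | Subjects moved | Rate in maximum-severity table | Chance of at least one moved |
|---|---|---|---|
| 1% | 0.09 | 3.76% | 0.084 |
| 5% | 0.44 | 3.61% | 0.354 |
| 10% | 0.87 | 3.42% | 0.583 |
| 20% | 1.75 | 3.04% | 0.827 |

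In every row the rate in the adverse event overview stays at 3.80%.

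**The case against.** **The rule is deliberate and coherent.** If one occurrence is ungraded, the true maximum is strictly unknown unless another occurrence already has the top grade. The relationship table in SAP 7.2 is built the same way, with only the top category overriding unknown, and a programmer could read the missing-grade sentence as a specific exception to the general one. Part of this stands: the intent can be guessed. It does not justify the result for Grades 3 and 4. Protocol 6.1 defines Grade 5 as death related to the event, and the SAP reports deaths and fatal events separately. If the ungraded occurrence was not fatal, the maximum of Grade 4 and ungraded is Grade 4. The relationship scale in Protocol 6.1 has only two categories, so protecting the top one is enough. Severity has five grades, so it is not.

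**The trial's severe-event rate is unaffected.** A reader might infer that the SAP understates severe adverse events overall. The documents do not support that. The three sets of Grade 3 or higher summaries still count the subject, and the subject remains visible under unknown.

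**The rule does not always flatter the drug.** A reader might infer that the error is favourable throughout. It is so only in the Grade 3 and 4 rows of these tables, measured against the highest known grade. Moving a subject with Grade 1 or 2 and an ungraded occurrence to unknown avoids calling that subject mild. Scoring such a subject at the known grade would itself be a favourable assumption.

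**It may never happen.** It takes a Grade 3 or 4 event, a second occurrence of the same event in the same subject, and a blank grade, when Protocol 6.1 and SAP 7.2 both expect every event to be graded. This stands, and it limits the point's weight.

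**Conclusion.** The point holds for the maximum-severity summaries of all and of drug-related treatment-emergent events, and for nothing wider. There, a known Grade 3 or 4 is replaced by unknown. The rule conflicts with the general counting sentence in the same section, and the tables can disagree with the Grade 3 or higher summaries.

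The numerical effect is probably small: fewer than two subjects on average, even at an assumed 20% share. That range is only an illustration. The share is not in the documents, and the 3.8% comes from a programme that included compensated cirrhosis and advanced kidney disease (Protocol 2.1). This trial excludes subjects with evidence of cirrhosis or creatinine clearance below 30 mL/min (Protocol 5.1). No safety hypothesis or success criterion depends on these tables; the criteria in SAP 6.2 and 6.3 concern SVR12 only.

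The case for changing the text therefore rests on the inconsistency and the loss of established information, not on a predicted bias.

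**What to change.** In SAP 7.2, under Adverse Events by Maximum Severity Grade Level:

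1. Let any known Grade 3, 4 or 5 occurrence override unknown, and count the subject at the highest known grade for that event.
2. Keep unknown for a subject with no graded occurrence of the event.
3. For Grade 1 or 2 with an ungraded occurrence, choose one convention and state it: keep unknown, or report the known grade with a footnote.
4. Footnote every subject who has both graded and ungraded occurrences of the same event.
5. Cross-refer the general counting sentence and the missing-grade sentence, so that it is clear which applies when a grade is missing.

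The cost is a short text edit and a change to the program for these tables. No new data are needed, and no other analysis changes.

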7.3 Analysis of Laboratory Data

Data collected from the central and local laboratories, including additional laboratory testing due to an SAE, will be used in all analyses. The protocol-defined hematology, clinical chemistry, and urinalysis laboratory tests will be summarized. Some of the above laboratory variables are calculated by the laboratory vendor including indirect bilirubin, creatinine clearance, and eGFR by MDRD.

The baseline value for clinical laboratory tests will be the last non-missing measurement on or before the day of the first dose of study drug. Values on Day 1 must also be before the time of first dose if time is available. The same baseline value will be used for change to Treatment Period visits and change to Post-Treatment Period visits.

Mean changes from baseline to each post-baseline visit, including applicable post treatment visits, will be summarized. Each protocol-specified laboratory parameter will be summarized with the sample size, baseline mean, visit mean, change from baseline mean, standard deviation, minimum, median, and maximum.

The laboratory parameters defined in [Table 1](#) will be assigned a toxicity grade of 1, 2, 3, or 4. The number and percentage of subjects with a maximum toxicity grade of 1, 2, 3 or 4 will be summarized.

Table 1. Definitions of Toxicity Grades 1, 2, 3, and 4 for Laboratory Values

Test	Grade 1	Grade 2	Grade 3	Grade 4
ALT	> ULN – 3 × ULN	> 3 – 5 × ULN	> 5 – 20 × ULN	> 20 × ULN
AST	> ULN – 3 × ULN	> 3 – 5 × ULN	> 5 – 20 × ULN	> 20 × ULN
Alkaline Phosphatase	> ULN – 2.5 × ULN	> 2.5 – 5 × ULN	> 5 – 20 × ULN	> 20 × ULN
GGT	> ULN – 2.5 × ULN	> 2.5 – 5 × ULN	> 5 – 20 × ULN	> 20 × ULN
Total Bilirubin	> ULN – 1.5 × ULN	> 1.5 – 3 × ULN	> 3 – 10 × ULN	> 10 × ULN
Hemoglobin	< LLN – 100 g/L	< 100 – 80 g/L	< 80 g/L	--
White blood cells	< LLN – 3.0 × 10 ⁹ /L	< 3.0 – 2.0 × 10 ⁹ /L	< 2.0 – 1.0 × 10 ⁹ /L	< 1.0 × 10 ⁹ /L
Absolute Neutrophil Count	< LLN – 1.5 × 10 ⁹ /L	< 1.5 – 1.0 × 10 ⁹ /L	< 1.0 – 0.5 × 10 ⁹ /L	< 0.5 × 10 ⁹ /L
Platelet count	< LLN – 75.0 × 10 ⁹ /L	< 75.0 – 50.0 × 10 ⁹ /L	< 50.0 – 25.0 × 10 ⁹ /L	< 25.0 × 10 ⁹ /L
INR	> 1 – 1.5 × ULN	> 1.5 – 2.5 × ULN	> 2.5 × ULN	--
Glucose (increased)	> ULN – 8.9 mmol/L	> 8.9 – 13.9 mmol/L	> 13.9 – 27.8 mmol/L	> 27.8 mmol/L
Glucose (decreased)	< LLN – 3.0 mmol/L	< 3.0 – 2.2 mmol/L	< 2.2 – 1.7 mmol/L	< 1.7 mmol/L
Creatinine	> ULN – 1.5 × ULN	> 1.5 – 3 × ULN	> 3 – 6 × ULN	> 6 × ULN
Creatinine clearance	< LLN – 60 mL/min	< 60 – 30 mL/min	< 30 – 15 mL/min	< 15 mL/min
Albumin	< LLN – 30 g/L	< 30 – 20 g/L	< 20 g/L	--

Assessment of Hepatotoxicity

The number and percentage of subjects with maximum on treatment lab values meeting the following criteria for potential hepatotoxicity will be summarized:

- ALT $\geq 3 \times$ ULN and total bilirubin $\geq 2 \times$ ULN;
- ALT $\geq 3 \times$ ULN and total bilirubin $< 2 \times$ ULN;
- ALT $> 5 \times$ ULN and total bilirubin $< 2 \times$ ULN;
- ALT $< 3 \times$ ULN and total bilirubin $\geq 2 \times$ ULN.

The number and percentage of subjects with post-baseline values during the Treatment Period meeting the following criteria for hepatic laboratory parameters will be summarized:

- ALT > 5 × ULN and ≥ 2 × baseline;
- AST > 5 × ULN and ≥ 2 × baseline;
- Total bilirubin ≥ 2.0 × ULN and > baseline.

